This method of recruitment and sampling limits the amount of information to be collected each month, enables the tracking of patients each month to maintain the open cohort within each clinic, it simplifies the sampling process, and maintains patient confidentiality.

[figure not shown]
The research participation response rate experienced by our partners range from 60-80% and we will sample 30 patients each month to achieve our target sample of 20 per month.

Methods: Assignment of interventions

A number of outcomes will be collected by interviewing a random sample of 20 patients who have received a consultation in the previous month. To reduce the transfer of patient identifiable data and their contact details, we specify the following sampling protocol. On the first calendar day of each month the list of patients who have had at least one consultation in the preceding month will be aggregated within each cluster site by the facility representative. The list will be pseudonymised by redacting identifiable information including patient name and contact details but keeping unique IDs, such as row numbers, and other basic data to permit comparisons between sampled and interviewed

groups for quality control. The list will be photographed and sent to the trial statistician, who will send back a random sample. Data collection from the selected patients can then proceed.

Figure 1: Cluster randomisation sequencing

Allocation

Within each country the 20 participating clusters will be randomised to one of ten sequences (see figure 1) with two per sequence. A random number will be generated for each cluster and then clusters assigned to each sequence in ascending order of the generated number. The randomisation will be conducted by the trial statistician who will be blinded to cluster name. The intervention implementers and clinics will not be blinded to allocation sequence as this is impractical given the need to plan and prepare training.

Blinding

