In each local trial delivery team, one investigator and 1 research assistant will remain blinded to the month during which REaCH training was delivered to each cluster. Each facility is given a unique identification number consisting of 4 digits. We use four digits to make it more difficult for the research team to recall cluster IDs when discussing with the unblinded education team. This will reduce bias when monthly data collection is undertaken. When education and research teams meet together, clusters will be referred to by identification number only. At the beginning of every data collection activity the researcher will remind the health worker or patient participant not to reveal whether the facility has undertaken REaCH training. Data entry will be undertaken by a database assistant who will be blinded to whether the data is from a cluster in the intervention or the control. At the bi-weekly trial team meetings we will have an agenda item to check with every blinded member whether they think they have been unblinded in relation the identity of a randomised cluster during the previous two weeks. All UK investigators will be blind to cluster randomisation except the Birmingham trial statistician.

Methods: Data collection, management, and analysis

Trial data collection methods

At trial set up each cluster will provide the research team with a pseudonymised whole facility population of eligible patients. This is the open cohort. On the same day/date of every month the clinic will provide the research team with four lists:

- 1) A list of pseudonymised patients who had face to face consultations since the last data period
- 2) A list of pseudonymised patients who had remote consultations since the last data period
- 3) A list of pseudonymised patients who had prescriptions ordered and collected since the last data period
- 4) A list of pseudonymised patients who had investigations ordered since the last data period

From the combined monthly lists of 1 and 2, the research team will generate a random order list of 30 pseudonymised patients to sample for completion of the patient reported outcome data. Once informed consent procedures are completed, the researcher will undertake a structured interview with the participant by telephone to complete the two questionnaires.

Table 1: Complete listing of the trial data collected

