In all trial clusters we will survey facility managers and tier 1 trainees on implementation one month after completion of the REaCH training for the cluster. The timing allows them time to have reflected on the training and start planning delivery. The questionnaire provides the participant opportunity to reflect on implementation. We will collect information on how facilities distributed the airtime allowance across tier 1 and tier 2 trainees.

Observation, interview and prescription data will be collected in each country, from a random sample of five facilities (clusters) who receive the intervention during the first 6 months of the trial, to allow time for implementation prior to data collection.

Consent to process evaluation data collection will be taken along with consent to trial participation.

Training data (all clusters)

Prior to each REaCH training the facilitator will confirm consent to the use of aggregate data about the trainees/training and to the use of trainees' text for analysis in the study process evaluation clarifying that all personal identifiers will be removed before it is shared with the research team. This will be repeated at the end of the training. Trainees will be able to confidentially inform the facilitator if they do not wish their text to be included.

Survey of facility manager and trainees (all clusters)

All tier 1 trainees and the facility manager in all clusters will be invited to complete a questionnaire about implementation of remote consulting.

Observation (2x5 clusters)

We will observe two tier 1 and two tier 2 training sessions. Each REaCH facilitator will provide us with their timetable for training delivery. We will take a stratified random sample of planned training sessions to ensure observation of the range of modules within the training. Where individuals scheduled to attend observed training sessions have not given consent to be observed we will discuss with them their options. They may choose to attend but remain silent or they may choose not to attend. They will be offered a briefing session with the facilitator after the session so they are able to catch up on learning.

Semi-structured telephone interviews (2x5 clusters)

We will interview 3-4 months after training

- the facility manager
- the REaCH facilitator
- two tier 1 and two tier 2 health workers
- four patient trial participants

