In Tanzania and Nigeria more men than women own a mobile phone. The difference in ownership differs by country and across Africa as a whole, the difference is 8% fewer women owning mobile phones [26]. The potential impact of this is that women may have less access to remote consultations. If they have less access they may travel to health centres for face to face health care which puts them and their health workers at risk. Whilst fewer women own a mobile phone the majority have access either to a family phone or a fixed landline in the community [27]. To ensure that our research does not disadvantage women we will monitor recruitment within each cluster by sex. Where we find a difference in the sex of participants of greater than 10% this will trigger an over sampling in the process evaluation of the sex least represented so that we can understand the issue for women. The stepped-wedge trial designs means that we can monitor this and make changes to our trial procedures as we deliver REaCH training to subsequent health facilities to try and understand and address any sex imbalance that we find. However, the breadth of women's phone use is also narrower. REaCH training is intended to result in people having a trustworthy and safe experience of remote consulting with health workers and such experience may expand women's often self-restricted use of mobile services in general [26].

Protocol amendments

Protocol amendments with ethical implications will be subject to approval by all three ethical committees approving the trial. The proposed protocol amendments will not be implemented without prior ethical approval.

Consent or assent

All participants will undertake an informed consent process with information provided in written and spoken local languages and consent recorded in writing or verbally audio-recorded.

Confidentiality

Each participant's personal details will be linked to their study identifier in an excel spreadsheet that five members of the investigator team will have access to. This document will be password protected and encrypted. Responsibility for managing this database will be held with the Ibadan Trial manager and the database will be held on a secure Ibadan server. All data collection and recording will be GDPR compliant.

Declaration of interests

All investigators will register any conflicts of interest with the KCL PI and the KCL Trial Manager.

Ancillary and post-trial care

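### The safeguard for women's access to remote care monitors who is recruited, not who gets remote care, and its trigger can send the extra interviews to men

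*Protocol*

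**What the plan says.** In the protocol, Ethical Issues, Sex-based equality, the harm is named in two steps. Because fewer women own phones, "The potential impact of this is that women may have less access to remote consultations", and "If they have less access they may travel to health centres for face to face health care", which the protocol regards as a risk to them and to health workers.

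The safeguard is that "we will monitor recruitment within each cluster by sex". The rule follows: "Where we find a difference in the sex of participants of greater than 10% this will trigger an over sampling in the process evaluation". The target of that oversampling, and the reason for it, are then given in these words: "of the sex least represented so that we can understand the issue for women". The paragraph adds that trial procedures may be changed as training reaches later facilities. It does not say what the 10% is measured against, over what period, or with what minimum count.

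Three other places fix how the rule would work:

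- **Who is recruited.** Under Trial data collection methods: "From the combined monthly lists of 1 and 2, the research team will generate a random order list of 30 pseudonymised patients". Lists 1 and 2 are the face-to-face and the remote consultations.
- **Where interviews happen.** The process evaluation interviews four patients in each of five clusters per country, 3-4 months after training.
- **What is already held.** Patient participant recruitment and sampling gives the team sex by patient ID for the open cohort, and visits by type each month by the same ID.

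**The concern.** An equity safeguard should respond when the harm occurs, stay mostly quiet when it does not, and lead to an action that helps the group at risk. This one is doubtful on all three counts. The harm concerns the mode of care, but the indicator ignores mode. The threshold has no reference or window, so its false-alarm rate depends on how it is read. The action is tied to whichever sex is in the minority, while its purpose is tied to women.

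What is at stake is the credibility of the safeguard and the choice of a small number of interviewees. A real gap in women's remote access could go unseen while monitoring is being done as planned.

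**Working it through.** The protocol gives no operating characteristics for the rule, so there is no stated figure to reproduce.

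**Inputs from the protocol**

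- Recruits per cluster-month: 20 ("we will sample 30 patients each month to achieve our target sample of 20 per month"). With 60-80% response, 30 × 0.60 to 30 × 0.80 = 18 to 24, which is consistent.
- Months of data: 12, so 12 × 20 = 240 recruits per cluster.
- Baseline rates per person-month: 0.25 face to face, 0.02 remote. One visit per person-year = 1/12 = 0.083 per month.
- 20 clusters per country, about 100 active patients each.

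**Assumptions.** Women's share of the cohort is not in the documents; 50% and 60% are used. Recruits are treated as independent.

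**Step 1. Does the recruited mix move when women lose remote care?** The probability of being on the combined list in a month is 1 − exp(−total rate). Start from a cohort that is half women.

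- *Replacement, the harm named.* Women have all visits in person at 0.27. Men have 0.25 − 0.083 = 0.167 in person plus 0.02 + 0.083 = 0.103 remote, total 0.27. Both give 1 − exp(−0.27) = 0.237, so women are 50.0% of attenders and the trigger probability is the same as with equal access.
- *Women lose the baseline 0.02, not replaced.* 0.221/(0.221 + 0.237) = 48.3%, a gap of 3.4 points, below the threshold.
- *Remote visits purely extra and only for men.* Men's total is 0.25 + 0.103 = 0.353, giving 0.297. Women are 0.221/(0.221 + 0.297) = 42.7%, a gap of 14.7 points. On the gap reading the trigger fires with probability 0.589 at n = 20 and 0.749 at n = 240.

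**Step 2. Chance firing.** Let X be the number of women among n recruits, binomial(n, p). The gap reading fires if |2X − n|/n > 0.10. The deviation reading fires if |X/n − 0.5| > 0.10. For n = 20 these mean X ≤ 8 or X ≥ 12, and X ≤ 7 or X ≥ 13.

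| True share of women | Reading | n = 20 | n = 240 |
|---|---|---|---|
| 50% | gap between the sexes | 0.503 | 0.106 |
| 50% | deviation from 50% | 0.263 | 0.002 |
| 60% (assumed) | gap between the sexes | 0.652 | 0.935 |
| 60% (assumed) | deviation from 50% | 0.437 | 0.475 |

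**Step 3. Direction of the action.** With 60% women and no access problem, the rule fires and selects men with probability 0.596 (n = 20) or 0.935 (n = 240) on the gap reading, and 0.416 or 0.475 on the deviation reading. At a true 50/50 mix, half of all chance triggers select men.

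**Step 4. Reach.** Monitoring is in every cluster, but 20 − 5 = 15 clusters per country have no patient interviews to oversample. The interviews number 5 × 4 = 20 patients per country.

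**Step 5. What a rate-based indicator could do.** Assume half the cohort are women and about six post-training months per cluster. Each sex then has 20 × 50 × 6 = 6,000 person-months and 6,000 × 0.02 = 120 remote visits per country. SE(log ratio) = √(1/120 + 1/120) = 0.129. The ratio detectable with 80% power at two-sided 5% is exp(−2.80 × 0.129) ≈ 0.70, ignoring overdispersion between patients.

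A monthly cut at 10% would not work. With equal access and Poisson counts, women's pooled rate falls more than 10% below men's in 40% of months with 10 trained clusters (10 × 50 × 0.02 = 10 visits expected per sex) and 37% with 20. At a remote rate of 0.103 the figures are 30% and 22%.

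**The case against.** The strongest reply is that the paragraph leaves the rule open rather than fixing it wrongly. A reader might infer that the reference is equal numbers, that the window is one month, and hence that the rule fires mostly by chance or permanently in a majority-female cluster. The documents support none of these as fact. The sex of the whole eligible cohort is held, and under Assignment of interventions basic data are kept to compare sampled with interviewed patients, so the team could compare recruits with their own cohort. Interviews come 3-4 months after training, so cumulative counts are at least as natural as monthly ones, and chance then plays a smaller part. This stands. The figures above are therefore conditional on the reading.

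A reader might also infer that the indicator can never reflect unequal access. That goes too far. Sampled patients are first contacted by mobile phone, so a phone gap could lower women's recruitment directly, and step 1 shows that the mix can move if remote visits are extra and go almost wholly to men. Such a shift could not, however, be told apart from cohort make-up without a cohort reference.

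The five-cluster limit applies only to oversampling. The permitted procedure changes reach later clusters too. Finally, the rule touches no primary outcome or harms trigger.

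What the reply does not remove is that visit mode, which defines the harm, is not in the indicator, and that the action follows the minority sex whereas the aim is to learn about women.

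**Conclusion.** The point holds as a minor finding. For the harm the protocol itself names, women attending in person instead of remotely, the indicator does not respond: under one-for-one replacement and equal reachability by phone, the recruited mix stays at 50.0% and the trigger fires only at its chance rate. That rate ranges from 0.50 to 0.002 according to a reading and a window the protocol does not give. If the rule is read against equal numbers and women are the majority, it tends to direct oversampling to men. At an assumed 60% women this happens with probability 0.94 on the gap reading and about 0.48 on the deviation reading with 240 recruits.

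It would be wrong to infer that the trial's effect estimates are compromised. The consequence is confined to the equity safeguard, the choice of interviewees, and any procedure change that a misleading trigger might prompt.

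**What to change.** Reword the paragraph so that the indicator is, first, remote consultations per active woman against remote consultations per active man and, second, the remote share of all consultations by sex. Pool over trained clusters, cumulate over months, and report the rate ratio with its confidence interval to the TSC and DMEC. The interval should allow for repeat visits by the same patient and for clustering. Do not set a month-by-month 10% cut.

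State that women are the sex to oversample, in the interviews still to be held, when their remote rate is the lower one. If recruitment by sex is monitored as well, compare it with the cluster's own eligible cohort, not with 50/50, and give the window.

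The cost is one paragraph and one extra table from data already listed. Table 1 names sex only in the set-up dataset, so confirm that it is also recorded for patients who join the cohort later. The limit should be stated: at the baseline remote rate only a fairly large gap, a ratio of about 0.70 over the whole trial, is detectable with 80% power. The shortened Tanzanian schedule in Appendix 5 would probably leave less follow-up than step 5 assumes.

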Appendix 1 shows the data flow for patient participants through the trial.

Statistical methods

The data from each trial will be analysed using a generalised linear mixed model framework standard for stepped-wedge cluster designs[16]. Data from each time point are considered a repeated cross-section given the difficulty linking observations between patients in different time periods. The primary outcomes are of two types: count data (the number of consultations by mode of delivery and the number of prescriptions) and a continuous score (the patient trust outcome). For the former we

specify the following log-linear model, for patient $i = 1, \dots, N$ in cluster $j = 1, \dots, J$ at time period $t = 1, \dots, T$ with number of events y_{ijt}^1 :

$$y_{ijt}^{(1)} \sim \text{Poisson}(\lambda_{ijt})$$

$$\lambda_{ijt} = N_{jt} \exp(\eta_{ijt}^{(1)})$$

where N_{jt} is the denominator population (i.e. the number of active patients in cluster j at time t) and η_{ijt} is the linear predictor. For the continuous outcome y_{ijt}^2 we specify:

$$y_{ijt}^{(2)} \sim N(\eta_{ijt}^{(2)}, \sigma^2)$$

The specification of the linear predictor in both models takes the form:

$$\eta_{ijt} = x'_{ijt}\beta + z'_{jt}\gamma + \delta D_{jt} + \alpha_j + \psi_{jt}$$

where x_{ijt} is a vector patient-level covariates, z_{jt} is a vector of cluster-level covariates, D_{jt} is an indicator equal to one if cluster j has the intervention at time t and zero otherwise, and $\alpha_j \sim N(0, \sigma_\alpha^2)$ and $\psi_{jt} \sim N(0, \sigma_\psi^2)$ are cluster, cluster-time and individual random effects respectively. The treatment effect of interest from the Poisson model is an incidence rate ratio, although we will also provide absolute treatment effects for context, and from the linear model we will report only absolute treatment effects.

Inference

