In Tanzania we will seek approval from:

National Health Research Ethics Review Committee
National Institute for Medical Research
[name]
[name]
Dar es Salaam, Tanzania
[contact]
[contact]
Email: [contact] ; [contact]

Exemplar participant informed consent documentation can be found in Appendices 2 and 3. The project has been peer-reviewed by the UKRI/GCRF/Newton Fund funding panel prior to making an award.

Ethical Issues

Privacy and confidentiality

The intervention promotes remote health consultations by mobile phone or fixed communal landlines by both patient and health care worker. This presents issues of privacy for both parties when engaging in a confidential health communication. The REaCH intervention training covers the issue of privacy for both partners. Health workers are trained to both ensure that the conversation is confidential at their end of the phone call. They are also requested to ask the patient at the other end of the phone whether they are receiving the call in a sufficiently private place to meet their needs. Our process evaluation will seek to understand how this is experienced in reality for both partners and the stepped wedge design affords us the opportunity to strengthen messages around privacy if we detect concerns.

Sex-based equality

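### The protocol allows trial procedures to change alongside the roll-out of training; if survey recruitment changes that way, the trust and PAM-13 analyses cannot separate the change from the training effect

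*Protocol*

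**What the plan says.** Protocol, Ethical Issues, Sex-based equality: the team states that "we will monitor recruitment within each cluster by sex". A difference "greater than 10% this will trigger an over sampling in the process evaluation of the sex least represented". The next sentence goes further. It presents the stepped wedge as a means to monitor imbalance and to "make changes to our trial procedures as we deliver REaCH training to subsequent health facilities", so as to understand and address it. The text does not say which procedures may change, when a change starts, or whether untrained and already trained clusters change too.

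The control on changes is under Protocol amendments: "Protocol amendments with ethical implications will be subject to approval by all three ethical committees approving the trial". This is an ethical safeguard and contains no rule on how a change is rolled out across clusters.

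Protocol, Statistical methods: the data are analysed in a "generalised linear mixed model framework standard for stepped-wedge cluster designs". The treatment term D_jt "is an indicator equal to one if cluster j has the intervention at time t and zero otherwise". There is one coefficient, delta, and no term for a version of procedures. The written predictor shows no explicit period term, although cluster-level covariates z_jt could hold one.

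A related sentence under Privacy and confidentiality says that "the stepped wedge design affords us the opportunity to strengthen messages around privacy if we detect concerns".

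**The concern.** In a stepped wedge, delta is estimated from what changes in a cluster when it crosses over, relative to clusters that do not cross over in the same month. A research procedure that changes as a later facility is trained is absent in that cluster's control months and present in its trained months. In that cluster it has the same pattern as D_jt. Period effects do not remove it, because it follows the step and not the calendar.

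Trust and PAM-13 are exposed because they come from patients who are sampled, approached by the facility and then consent: 30 are drawn per cluster-month to obtain 20, at an expected response of 60-80% (Patient participant recruitment and sampling). A change in how patients are approached or interviewed could alter who answers or how. The protocol expects no change in trust and has non-inferiority aims, so a modest artefact could create a difference or hide one. An analysis plan could not fully repair this afterwards, so the roll-out rule belongs in the protocol.

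**Working it through.** **Inputs.** From Sample size and Allocation: 20 clusters per country, 10 sequences of 2, ICC 0.05, CAC 0.8, power 80%, two-sided 5%, trust SD 0.5, n = 20 per cluster-month. From Participant timeline: data in months 2-13, which is 12 periods. Table 1 shows t = 1 to 13, so 11 to 13 periods were tried. Assumptions: one baseline month, one step per month, fixed period effects.

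**Variance components of a cluster-month mean.**
- cluster: ICC × CAC × SD² = 0.05 × 0.8 × 0.25 = 0.0100
- cluster-period: ICC × (1 − CAC) × SD² = 0.05 × 0.2 × 0.25 = 0.0025
- residual: (1 − ICC) × SD² / n = 0.95 × 0.25 / 20 = 0.011875

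**Reproducing the plan's figure.** Minimum detectable effect (MDE) = (1.96 + 0.84) × SE(delta), with SE from generalised least squares (GLS):
- 11 periods: SE 0.0270, MDE 0.0756
- 12 periods: SE 0.0263, MDE 0.0738
- 13 periods: SE 0.0258, MDE 0.0723

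The stated value is 0.07, which 12 or 13 periods reproduce after rounding.

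**Share of a procedure effect that enters delta.** The GLS estimate is a weighted sum of cluster-month means, with weights W_jt. If a changed procedure shifts the score by theta in the cluster-months marked M_jt = 1, the expected change in the estimate is theta × Σ W_jt M_jt. Three roll-outs were compared, with period effects fitted:

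| Roll-out of the change | From sequence 4 | From sequence 6 | From sequence 8 |
|---|---|---|---|
| At crossover, later sequences only: 11 periods | 0.68 | 0.43 | 0.20 |
| same: 12 periods | 0.72 | 0.48 | 0.25 |
| same: 13 periods | 0.74 | 0.52 | 0.29 |
| All already trained clusters from that month, later ones at crossover | 0.72 | 0.42 | 0.15 |
| All clusters, trained or not, in that month | 0.00 | 0.00 | 0.00 |

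With 12 periods and a start at sequence 6, the change covers 40 of 130 trained cluster-months (31%), yet 0.48 of its effect reaches delta. With two baseline months and 12 periods, the first row's shares are 0.64, 0.39 and 0.18.

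**Two readings of the table.** Extending a change to already trained clusters does not help; the untrained ones must change as well. The zeros in the last row also need period effects: without them, a same-month change in all clusters leaves 0.56 to 0.75 of its effect in delta.

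**The case against.** The protocol does not say that changes start at each cluster's crossover, or that early clusters never receive them. A reader might infer both, but the sentence can equally mean changes made during roll-out, and a change on one calendar date is harmless once period effects are fitted. The single concrete trigger leads only to over-sampling in the process evaluation, outside the trial outcomes. Sampling is central and random, and one investigator and one research assistant per country stay blinded to the training month, which works against cluster-by-cluster changes to the survey. These points stand. They make the bias conditional without closing the route: facility staff make first contact with sampled patients, the clinics are not blinded, and the sentence names trial procedures and links them to training of later facilities.

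A reader might also infer a spurious trust effect as large as the whole MDE. With 12 periods and a start at sequence 6 that needs a shift of 0.0738 / 0.48 = 0.15 points, for which the documents give no basis. Through sex mix alone, a 10-point change in composition would need a gap between men and women of 0.15 / 0.10 = 1.5 points, or 3 SD. Sex is recorded, and the model allows patient-level covariates, so that part can be adjusted for. What adjustment for sex cannot remove is a change in who responds within each sex, or in how answers are given.

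Finally, a reader might count the privacy sentence as the same fault. It is not: "The REaCH intervention training covers the issue of privacy for both partners", so the effect of stronger messages is properly an effect of training.

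**Conclusion.** The point holds conditionally. The protocol gives an open permission to change trial procedures in step with training. If survey recruitment or data collection is changed that way, a single-indicator model with period effects cannot separate the change from the training effect on trust and PAM-13. Under the original 10-sequence design with one baseline month and 11 to 13 periods, about 0.2 to 0.74 of the resulting shift enters delta for starts between sequences 4 and 8, and 0.43 to 0.52 from sequence 6. The shift itself is unknown and may be zero.

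The two consultation rates and the prescribing rate are taken from clinic lists covering all active eligible patients, so three of the four primary outcomes are largely unaffected. The figures do not carry over to the six-sequence Tanzania redesign in Appendix 5, although the mechanism is the same. Strengthened privacy messages are not a source of bias; they mean only that delta averages over versions of the training.

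**What to change.** Amend the sentence under Sex-based equality to say that any change to recruitment, sampling or data-collection procedures for trial outcomes starts in all clusters of a country in the same calendar month, whatever their training status, that the date is recorded, and that the analysis fits period effects. The team can still act on sex imbalance.

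For the privacy messages no procedural change is needed; describe delta as an average over the versions of training delivered.

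The cost is protocol wording. The one downside is that a procedural change can no longer be phased in facility by facility.
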